## Project Q Pilot

### PURPOSE OF THE STUDY

The purpose of this pilot study is to evaluate the feasibility, acceptability, and preliminary efficacy of an intervention to promote smoking cessation among light daily and intermittent smokers. The intervention will include a combination of cognitive-behavioral cessation counseling and cue exposure treatment. This pilot study aims to test tailored intervention strategies for light smokers. We will use data from this pilot as preliminary data for a P01 grant application we will resubmit to the National Cancer Institute in January 2020.

### BACKGROUND & SIGNIFICANCE

Light daily and intermittent smokers (smoking  $\leq 10$  cigarettes per day or on some days) now represent almost half of all people who smoke; yet, smoking even a few cigarettes a day or even on some days increases morbidity and mortality. Despite this, light smokers continue to be excluded from most cessation trials. Further, exclusion of light smokers from cessation trials contributes to health disparities as many light smokers are African American or Latinx, who suffer more from smoking-related diseases than Whites. Thus, researchers have been attempting to design interventions to help light smokers quit with some but limited success. We argue that we do not understand enough about why light smokers have a different pattern, and therefore, cannot find effective ways to help them quit. Also, there are subgroups of light smokers. Some light smokers have always smoked 10 or fewer cigarettes a day (i.e., native light smokers) whereas others were formerly heavier smokers but now are light smokers (i.e., converted light smokers). To date, most researchers have designed interventions for light smokers that mimic those found effective for moderate to heavy smokers. These interventions have been based on the two-factor model for smoking behavior, addressing both nicotine dependence and situational and environmental responses to cues to smoke. Thus, the interventions included pharmacological agents that principally attenuate nicotine withdrawal effects or make nicotine less rewarding and behavioral and cognitive components that teach coping skills to overcoming urges in response to cues as well as increasing self-efficacy, outcome expectations, and problem-solving skills. However, these interventions have had limited success with light smokers. Different approaches might be necessary to help light smokers quit.

This pilot will build upon the hypothesis that while nicotine dependence may still play a role in light smoking, situational and environmental cues primarily drive light smoking. Thus, focusing on cue reactivity rather than just addressing nicotine dependence might be more effective at promoting cessation among light smokers. The behavioral aspect of cognitive-behavioral treatments might be more important for light smokers.

Thus, effective cessation programs for light smokers need to incorporate traditional cognitive strategies that promote self-regulation, behavioral learning strategies to optimize the ability to unlearn smoking cues, and elements to increase motivation, decrease barriers, increase self-efficacy and improve outcome expectations.

In this small, randomized controlled pilot trial, we will test the feasibility, acceptability, and preliminary efficacy of a combination of cognitive behavioral cessation counseling and cue exposure treatment, a cue driven treatment that has been found effective in the treatment of substance use. Further, we will extend cue exposure therapy beyond the clinic or laboratory by using interactive texting to help light smokers transfer their newly learned cue extinction skills into their natural environment. Interactive

texting will include both self-monitoring and extinction of cue extinction skills. Interactive texting for real-time data collection will include participants taking photographs of cues they identify as salient and triggering of their desire to smoke as well as texting when they smoke and their craving levels. We will incorporate the participants own photographs into their tailored cue exposure treatment conducted in the clinic

#### ***Specific Aims***

**Aim 1:** To assess the feasibility of an enhanced cue exposure therapy intervention. This aim will specifically address the number of participants recruited and the number of participants who complete all study visits.

**Aim 2:** To evaluate and compare the acceptability of cue exposure therapy compared to standard smoking cessation counseling and support text messages as measured by participants' ratings of the usefulness of the intervention.

**Aim 3:** To compare the preliminary efficacy of an enhanced cue exposure therapy compared to standard smoking cessation and support messages in light smokers as measured by a) self-report 7-day point prevalence abstinence from smoking and b) biochemically validated smoking cessation.

### **DESIGN & PROCEDURES**

#### ***Design***

The two-arm trial compares Arm 1) standard smoking cessation counseling and 2) enhanced cue exposure treatment. For all arms, we will conduct a phone screening, provide smoking cessation counseling, and an in-person follow-up visit. The primary outcome will be feasibility and acceptability. The secondary outcome will be biochemically-validated cessation 1-week post-intervention.

#### ***Consent Process***

Study staff will call people who express interest in the study and conduct a phone screening. Those eligible will be asked to come in-person to consent and complete the baseline visit. Study staff will meet potential participants to obtain informed consent.

#### ***Data Collection Methods***

For all arms:

The baseline survey will include questions about demographics, smoking factors, and household information. The follow-up surveys will include some of the same questions as the baseline as well as process questions to assess helpfulness of the messages and participants' fidelity to the intervention protocol. The primary outcome will be assessed using seven-day point prevalence abstinence (e.g., Have you smoked any cigarettes in the past 7 days?) and biochemically validated through saliva analysis.

***Saliva samples:*** Saliva samples from participants at baseline and follow-up will be used to biochemically validate the participant's smoking status. NicAlert strips will be used to measure the cotinine levels in the saliva at baseline and follow-up.

***Text-message real-time data collection:*** We will ask participants in Arm 2 to text study staff every time they smoke and every time they have a strong urge to smoke for four consecutive days. The system will ask participants to rate their level of craving (1-10) and stress (1-10) via text. We will also ask participants in Arm 2 to take and text several photos of the situation in which they smoked/had the urge to smoke. Additionally, we will ask all participants to text the system every time they feel like smoking or

have an urge to smoke between Visits 2 and the follow-up visit. The system will ask the same questions about craving and stress but participants will not be asked to text a photo. For Arm 2 participants, the system will reply with a supportive message to encourage the participant not to smoke along with the questions. Participants will be instructed not to text while driving and only to text when it is safe to do so.

*Cue exposure therapy measures:* Participants will sit in front of a computer screen while the screen shows a PowerPoint presentation composed of a repeating set of images. Each set will include standardized smoking images and images that have been shown to make people who smoke want to smoke. These images will be from the International Affective Picture System (IAPS), a database of images designed to provide a standardized set of pictures for studying emotion and attention. Also, we plan to use 4-6 of the smoking images that participants have sent themselves. We will only show participants their images, not images taken by other participants. Additionally, participants will also be exposed to in vivo cues by following instructions to touch/hold/smell smoking paraphernalia, including cigarettes, ashtrays, and lighters.

A participant can miss completing any time point/study visit and it is not considered a protocol deviation.

## **STUDY INTERVENTIONS**

### ***Randomization***

We will randomize participants into one of two arms: Arm 1) standard smoking cessation counseling and 2) enhanced cue exposure treatment. The randomization will be automated and drawn from a random number generated list programmed onto the laptops. We will stratify randomization on the number of cigarettes per day and native /converted smoking status.

### ***Intervention and Control Activities***

Study staff will meet with all enrolled participants to conduct standard smoking cessation counseling (Visit 1: Baseline). At Visit 1, all participants will receive standard smoking cessation counseling, be asked to select a quit date. All participants will receive detailed instructions on how to collect real-time data on their smoking habits and craving levels. Arm 2 participants will be asked to identify smoking cues that they will photograph and also will receive detailed instructions on how to take and send pictures. Participants will select 4 consecutive days for collecting real-time data.

After Visit 1, participants in Arm 2 will text the study phone number every time they smoke for 4 consecutive days. The system will text questions related to the smoking encounter to the participant. Arm 2 participants will text a photo of the context in which they smoked. These photos will be used in in-person cue exposure therapy.

### **Visit 2**

#### **Arm 1 and 2 participants:**

At Visit 2, all participants will meet in person with study staff to receive tobacco cessation counseling. All participants will complete a brief smoking assessment. Study staff will conduct smoking cessation counseling for both arms. The system will text the participant to collect data about the cue and the outcome. Questions include if the participant smoked or not, craving level, and stress level. Participants are instructed to continue to text the system up to the follow-up visit (approximately 4 weeks total).

### Visit 2:

#### Arm 2 participants only:

Study staff will review a summary of their real-time smoking data and then explain the process for cue exposure therapy. Participants will first complete a brief assessment including a questionnaire of smoking urges (QSU) (10 items), Minnesota Nicotine Withdrawal Scale (MNWS) (10 items), and the Positive and Negative Affective Schedule (PANAS) (20 items). Study staff will then explain the process for cue exposure therapy.

Participants will sit in a room lit with a table lamp. They will sit in a comfortable chair in front of a computer screen to watch the presentation. The presentation will include repeating blocks of images. The image blocks include a mixture of standard photos and the individual's photos. After each block, the participants will see a slide instructing them to uncover a tray located in front of them that contains cigarettes, ashtray and lighter. They will be instructed to touch/hold/smell smoking paraphernalia on the tray. After approximately 2 minutes, they will be instructed to cover the tray.

After completing the cue exposure treatment (CET), the study staff will review how they can apply these processes outside the lab setting when the participant faces a cue to smoke over the next month. Each image viewed in the CET presentation will have a simple logo with words in the bottom right-hand corner. This image will be used as a retrieval cue to remind participants of the CET experience when in the real-world setting. Participants will be instructed to text the team anytime they feel an urge to smoke and need support to not smoke at that moment. The system will send the retrieval cue along with a supportive message.

### Visit 3

#### Arm 1 and 2 participants:

After approximately one week, all participants will return for Visit 3. The procedures will be the same as Visit 2, completing the brief smoking assessment and standard smoking cessation counseling. Visit 3 is the last counseling session for Arm 1 participants.

#### Arm 2 participants:

Participants will also complete cue exposure therapy. This process repeats so participants will come in on a weekly basis for a total of 4 treatment visits (Visits 2, 3, 4, and 5) and will complete the same process as described for Visit 2.

### Follow-up

For the final visit, participants from all arms will return to the Tobacco Cessation Lab to complete the follow-up assessment. This will occur one week after Visit 5 and one week after Visit 4, respectively. They will complete a questionnaire and we will assess abstinence via 7-day point prevalence.

Participants will provide a saliva sample to biochemically validate their smoking status based on their cotinine levels. At the follow-up visits, we will ask participants if we can contact them after to ask for feedback on the pilot study. If they agree, we will call them or meet them in person to ask for their input.

Participants may also be asked at the time of visits to be audio-recorded for data or quality assurance purposes. They can refuse to be audio-recorded and can still participate in the study.

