## **SUBJECT RECRUITMENT & COMPENSATION**

### ***Screening and Recruitment***

We will recruit participants into this low-risk study through Duke Center for Smoking Cessation, Facebook, flyers in public locations, DukeList, Duke Primary Care clinics through the Primary Care Research Consortium, and Durham Public Housing.

Staff will conduct the study in Hock Plaza. When participants call to express interest in a research study, staff will screen them for the study.

At participating clinics in Durham, Wake, Orange, and Chatham counties, with a HIPAA Waiver of Authorization, DHTS will conduct a DEDUCE query to identify potentially eligible patients. We will send patients who report tobacco use of "Light tobacco smoker" and/or "Current everyday smoker" "Smokes some days" a letter from their provider informing them of the study and asking them to call a study phone number if they prefer not to be contacted about study participation. If an email address is accessible for these patients, we may also attempt to email them these documents. We will call or text people who do not call to refuse to screen them for eligibility and set up a screening visit.

The Center for Smoking Cessation and the Nursing School will post Facebook ads through their Facebook accounts. The Facebook ad includes a link to a Qualtrics survey that asks the participant for their contact information. El Centro Hispano staff will refer light smokers to the Qualtrics link as well. Study staff will call those interested people who complete the Qualtrics survey to assess eligibility. The eligibility screening will: confirm a patient's age, smoking status, interest in quitting smoking, use of other tobacco products, pregnancy status, breastfeeding status, and history of serious adverse reaction to cycloserine in the past.

Participants can receive up to \$150 to complete all aspects of the study. Participants will receive \$50 for completion of surveys at Visit 1 and \$100 at the follow-up visit. Participants will not receive

compensation for Visits 2, 3, 4 or 5 as these are intervention visits and we want the motivation to quit smoking to be intrinsic rather than extrinsic. Providing monetary compensation during these intervention sessions can interfere with this.

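### Arm 1's follow-up time is contradictory, and the Follow-up section sets the two arms' 7-day abstinence windows a week apart with no nominal overlap

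*Combined protocol and SAP*

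**What the plan says.** Five parts of the protocol bear on when abstinence is assessed.

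- **Follow-up** gives two times without naming arms: "This will occur one week after Visit 5 and one week after Visit 4, respectively". Abstinence is 7-day point prevalence, and a saliva sample is taken at the same visit.
- **Visit 3** ends Arm 1's counselling: "Visit 3 is the last counseling session for Arm 1 participants". Arm 2 continues "on a weekly basis for a total of 4 treatment visits (Visits 2, 3, 4, and 5"). No Visit 4 or 5 is described for Arm 1.
- **Design** sets the efficacy time without distinguishing arms: "The secondary outcome will be biochemically-validated cessation 1-week post-intervention".
- **Visit 2**, under a heading for both arms, says: "Participants are instructed to continue to text the system up to the follow-up visit (approximately 4 weeks total"). Data Collection Methods has all participants texting from Visit 2 until follow-up.
- **Screening and Recruitment** rules out "compensation for Visits 2, 3, 4 or 5 as these are intervention visits", without limiting those visits to one arm. Specific Aims describes the comparator as "standard smoking cessation counseling and support text messages".

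The section on Data Analysis & Statistical Considerations compares abstinence between arms by a chi-square or Fisher exact test with a 0.05 cut-off. It makes no adjustment for time of assessment.

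**The concern.** Seven-day point prevalence describes one particular week. If that week differs by arm, the comparison contains a time effect as well as a treatment effect. Because every participant in an arm would share the same nominal time, the analysis could not separate the two afterwards.

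Shifts in smoking status during the weeks in question are plausible. At Visit 1 participants are to "be asked to select a quit date", and Eligibility requires only that they want to quit within 30 days. Quits and relapses two to four weeks after Visit 2 are therefore to be expected in some participants.

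What is at stake is Aim 3, the preliminary efficacy comparison, whose results are intended to support a grant application. Design ranks cessation as secondary, although Data Collection Methods calls abstinence the primary outcome.

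**Working it through.** **Inputs.** Visit 3 comes about a week after Visit 2 for both arms, and Arm 2's Visits 2 to 5 are weekly (both under Visit 3). Taking Visit 2 as day 0, the nominal days are Visit 3 = 7, Visit 4 = 14 and Visit 5 = 21. The abstinence window is the 7 days before follow-up (Follow-up section).

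**The plan's own figure.** The Visit 2 section gives about 4 weeks of texting up to follow-up, for both arms. For Arm 2, Visit 5 + 7 = 21 + 7 = day 28, which is 4 weeks, so the figure reproduces. For Arm 1, placed after Visit 4 by the Follow-up section, 14 + 7 = day 21, which is 3 weeks, so it does not.

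**Follow-up time under each reading.**

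| Reading | Arm 1 follow-up (window) | Arm 2 follow-up (window) | Gap | Overlap |
|---|---|---|---|---|
| Follow-up section: Arm 2 after Visit 5, Arm 1 after Visit 4 | day 21 (14–21) | day 28 (21–28) | 7 days | 0 days |
| Follow-up section, arms in numerical order | day 28 (21–28) | day 21 (14–21) | 7 days | 0 days |
| Design, if the intervention ends at each arm's last session | 7 + 7 = day 14 (7–14) | day 28 (21–28) | 14 days | 0 days |
| Visit 2 section, about 4 weeks for both arms | about day 28 (21–28) | about day 28 (21–28) | about 0 | 7 days |

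The second row would place Arm 2's follow-up on the day of its own Visit 5, so the first row is the workable reading. The third row is conditional. Screening and Recruitment treats Visits 2 to 5 as intervention visits for unspecified arms, and Specific Aims gives the comparator text support. Against that, Data Collection Methods limits the supportive reply to Arm 2. The end of Arm 1's intervention is therefore itself unclear.

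**Does the first row equalise anything?** Time from Visit 2 is 21 days in Arm 1 and 28 in Arm 2. Time since the last session is 21 − 7 = 14 days in Arm 1 and 28 − 21 = 7 days in Arm 2. Neither is equal, so the rule does not serve as a deliberate alignment on either clock.

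**Effect on classification under the first row, with identical behaviour in both arms.**

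- Last cigarette on day 17: inside Arm 1's window (14–21), so counted as smoking. It is before Arm 2's window (21–28), so counted as abstinent there.
- Abstinent since before day 14, relapse on day 24: counted as abstinent in Arm 1 (assessed day 21) and as smoking in Arm 2 (assessed day 28).

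The first pattern favours Arm 2 and the second favours Arm 1. The documents give no quit or relapse rates and no sample size, so neither the net direction nor the size of the bias can be calculated.

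**The case against.** The strongest reply is that this is loose drafting and that no one chose different assessment times. The Follow-up section names no arm, and day 21 for Arm 1 requires an assumed Visit 4. The Visit 2 section and Data Collection Methods together point to about four weeks for everyone, in which case no timing bias arises. Other text also does not fit a two-arm trial without a drug, such as the three pairwise comparisons and the screening for cycloserine reactions, so the sentence may be left over from another design.

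Much of this is fair. The bias is conditional on the Follow-up section being followed, and the origin of the sentence is unknown. But that section is the one that schedules the assessment, and either order of arms gives the same 7-day gap. The four-week figure appears in an instruction about texting and does not override it.

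It is also true that visits are only approximately weekly. If Arm 1 came one day late and Arm 2 one day early, the windows would be days 15–22 and 20–27, sharing 2 days. Such drift produces partial overlap for some participants but not a common time point.

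Finally, this is a pilot that disclaims a definitive test of efficacy. That limits the consequence, although the plan still applies a 0.05 cut-off to the comparison.

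**Conclusion.** The concern holds. Arm 1's follow-up time is given inconsistently: day 21 under the Follow-up section, about day 28 under the Visit 2 section, and day 14 under a conditional reading of Design. Under the Follow-up section the arms are assessed 7 days apart, with windows that abut and do not overlap. The dates rest on a nominal weekly schedule counted from Visit 2. If the four weeks were counted from Visit 1, the 7-day difference would remain, so a single figure still could not fit both arms.

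Confidence is high for the contradiction and for the gap that the Follow-up section creates. No claim is made about the size or direction of bias. The feasibility and acceptability decisions do not depend on this point. It should be fixed because it affects the only randomised efficacy comparison.

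**What to change.** Assess 7-day abstinence and saliva cotinine in both arms at one scheduled time with the same permitted window, counted from randomisation (or from Visit 1 if randomisation takes place there). Set that time to coincide with Arm 2's planned follow-up, nominally day 28 from Visit 2, and apply it whether or not Visits 4 or 5 were attended. Because the interval from Visit 1 to Visit 2 is not stated, the protocol needs to give it so that the time can be expressed from randomisation. Name the arms in the Follow-up section, and bring Design, Visit 2, Visit 3 and Follow-up into agreement. This concerns outcome timing only and alters no session.

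The cost is protocol wording and an Arm 1 follow-up one week later than the Follow-up section implies (day 28 instead of 21), with no extra visit. There are two drawbacks. Arm 1 would be assessed 28 − 7 = 21 days after its last counselling session and Arm 2 28 − 21 = 7 days after, so the Design section's description of the time point must be reworded and the difference stated. The longer interval without a visit could also increase loss to follow-up in Arm 1. Missed visits are not deviations under Data Collection Methods, and the analysis section gives no rule for missing abstinence data, so follow-up completion should be reported by arm.
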